3.4.3 Exploratory Endpoints (Main Study)

(b) (6)
[Redacted text block containing multiple paragraphs of blacked-out content]

CCI [Redacted]

- █ [Redacted]
- █ [Redacted]
- █ [Redacted]
- █ [Redacted]
- █ [Redacted]
- █ [Redacted]
- █ [Redacted]
- █ [Redacted]
- █ [Redacted]
- █ [Redacted]
- █ [Redacted]

3.4.4 Endpoints for the Exploratory Study

For the exploratory study, as applicable, endpoints described in [Section 3.4.1](#), [Section 3.4.2](#), and [Section 3.4.3](#) will be assessed for Sequence 1 vs Sequence 2 as a post-hoc analysis. Results from the exploratory study will be analyzed separately from the main study results.

3.5 Study Procedures

3.5.1 Main Study: Schedule of Assessments

Study assessment time points for enrolled patients are summarized for the main study in [Table 3.5.1-1](#).

Procedures for enrolling patients into the study are described in [Section 3.5.1.2](#).

CCI [Redacted]

CCI
[Redacted]

Table 3.5.1-1 Main Study: Schedule of Assessments (for Patients Enrolled at Sites)									
	Screening ^a	Interventional Phase ^b				Mid-study (or End-of-study) Visit ^{c,d}	Optional 2nd Abilify MyCite Treatment ^d	End-of- study Visit ^e	CCI [REDACTED]
	≤13 days ^a	Baseline (Day 1) ^a	Day 30±7	Day 60±7	Day 90±7	Day 180±7	Days 180-≤360	Day ≤360±7	Days 1- 360
Study site visit	X	X				X		X ^e	
Informed consent	X								
Inclusion/exclusion criteria assessment	X								
Smartphone and data plan verification	X								
Demographic information and medical / psychiatric history		X							
Height and weight measured		X							
Vital signs		X							
Onsite onboarding with Abilify MyCite; patient pairs and applies patch		X							
Dispense patches, aripiprazole + IEM, and other supplies		X					X		
Physician reviews Abilify MyCite dashboard data every 2 weeks ^f			-----X ^f -----	-----X ^f -----	-----X ^f -----	-----X ^f -----	-----X ^f -----	-----X ^f -----	

Table 3.5.1-1 Main Study: Schedule of Assessments (for Patients Enrolled at Sites)									
	Screening ^a	Interventional Phase ^b				Mid-study (or End-of-study) Visit ^{c,d}	Optional 2nd Abilify MyCite Treatment ^d	End-of-study Visit ^e	CCI
	≤13 days ^a	Baseline (Day 1) ^a	Day 30±7	Day 60±7	Day 90±7	Day 180±7	Days 180-≤360	Day ≤360±7	Days 1- 360
CCI			■	■	■			■	
			■	■	■			■	
			■		■			■	
		■				■		■	
		■				■		■	
Concomitant medications									X ^h
Hospitalizations (all-cause and psychiatric)									X ^h
CCI									■

^aThe screening and baseline visits can be combined.

^bThe interventional period begins with the baseline visit and ends at the Day 180 visit (or early termination [ET] if the patient withdraws or is withdrawn from the study prematurely). Clinical data will be collected as part of routine clinical practice, not as a requirement for the protocol.

^cAll patients will complete the Day 180 visit. If a patient withdraws or is withdrawn from the study prematurely (eg, before completing the scheduled Day 180 visit), then an early ET visit should be performed, at which time all assessments and procedures that were to have been performed at the Day 180 visit should be completed. In such cases, the reason for the ET must be recorded.

^dAt the Day 180 visit, a second, optional interventional period (up to 6 months of Abilify MyCite; Days 180-≤360) may be initiated per the joint decision of the patients with their study physician. If the patient is not continuing in the optional second Abilify MyCite treatment period (Days 180-≤360), then the Day 180 visit is the final visit. Patients need to be on aripiprazole to use the system for the optional second treatment period.

^eThe Day 360 visit (and activities) are only completed for patients in the optional second Abilify MyCite treatment period (Days 180-≤360). If a patient withdraws or is withdrawn from the study prematurely (eg, before completing the scheduled Day 360 visit), then an early ET visit should be performed, at which time all assessments and procedures that were to have been performed at the Day 360 visit should be completed. In such cases, the reason for the ET must be recorded.

^fThe study physician is expected to regularly review the Abilify MyCite dashboard data during active Abilify MyCite use as consistent with routine care, approximately every 2 weeks. Note that “---x---” indicates an activity that occurs multiple times during the period.

^gIf a patient does not have a routine care visit at Day 30, Day 60, or Day 90, the scale will be administered by phone.

^hData collected if available per routine clinical practice ^{CCI} [REDACTED] at completion of the study (plus 3 months to allow for lag in ^{CCI} [REDACTED] patient data from baseline through end of study will be included. ^{CCI} [REDACTED]

3.5.1.1

CCI [REDACTED]

[REDACTED]

Data will also be collected from a virtual matched control group, as described in [Section 3.5.4](#).

3.5.1.2 Main Study: Enrollment Procedures

The study physician will make the decision regarding the patient's suitability for the study. The determination that a patient is appropriate for treatment with aripiprazole (regardless of whether or not they would switch from current treatment) and initiation of Abilify MyCite will be made prior to and independent of study initiation. Following the treating physician's determination of eligibility, patients will be approached for enrollment. As part of their routine office visits, patients will be approached for potential enrollment into the study by their treating physician.

3.5.1.3 Main Study: Screening

Eligibility assessment per the treating physician's decision and informed consent will be conducted during a screening visit up to 13 days prior to and including the baseline visit.

For patients enrolling into the study, those not on aripiprazole at screening will use the screening period for conversion to aripiprazole from other antipsychotics according to the approved labels.

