3.1.1 Main Study

The study design schematic for the main study is provided in [Figure 3.1-2](#).

This is a phase 4, open-label, prospective, pragmatic clinical trial to assess the difference between all-cause hospitalizations in patients using Abilify MyCite (for Months 1-3, then prohibited for Months 4-6) versus virtual matched controls from baseline to Day 180.

Virtual matched controls ^{CCI} [REDACTED] would be receiving treatment as usual (ie, any product other than Abilify MyCite, which may be oral aripiprazole or any other product).

Eligible patients will enter a screening period of up to 13 days. For patients enrolling into the study, those not on aripiprazole at screening will use the screening period for conversion to aripiprazole from other antipsychotics according to the approved labels. At the baseline visit (which may be the same visit as the screening visit), Abilify MyCite onboarding will be provided in the office, with commercial informational materials and additional call center support; then, patients will initiate 3 months of treatment with Abilify MyCite at the baseline visit.

During the following 3 months (Months 4 through 6), use of Abilify MyCite will be prohibited (and the patient continues with oral aripiprazole or other appropriate treatment, per routine clinical care). The primary endpoint will be assessed at Day 180. The final study visit will be on Day 180 for patients not continuing in the second, optional interventional period.

After the visit at Day 180, a second, optional interventional period (up to 6 months of Abilify MyCite) may be initiated per the joint decision of the patients with their study physician; patients in this second, optional interventional period will have a visit at Day 360 (in addition to their regular visits as clinically indicated). During this second, optional interventional period, patients may start and stop Abilify MyCite as clinically indicated.

Enrolled patients will be matched to a virtual control group identified from ^{CCI} [REDACTED] in a 1:3 ratio (enrolled patients on Abilify MyCite treatment versus virtual matched controls).

^{CCI} [REDACTED]
[REDACTED] the matching will be performed after the Abilify MyCite arm has been completed.

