3.3.4 Patient Inclusion Criteria

For enrollment into the study, patients are required to meet the following inclusion criteria:

Table 3.3.4-1 Inclusion Criteria	
1.	Patients are actively enrolled in an Anthem-affiliated commercial, Medicaid, or Medicare health plan with medical and pharmacy benefits.
2.	Male and female patients between the ages of 18 and 63 years, inclusive at the time of consent.
3.	Patients must have a smartphone with data plan.
4.	Patients must have a current diagnosis of SCH, BP1, or MDD.
5.	Patients currently prescribed aripiprazole, or appropriate for aripiprazole treatment.
6.	Within 60 days prior to study enrollment, patients are required to have had a hospitalization (all cause or psychiatric) or at least 1 psychiatric partial hospital admission.
7.	Patients are deemed appropriate, per the study physician judgment, to use Abilify MyCite per the package insert and to enter this interventional study.
8.	Patients must be able to read and understand English.

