3.4 Virtual Matched Control Group

Enrolled patients will be matched to a virtual control group in a 1:3 ratio (enrolled patients on Abilify MyCite treatment : virtual matched controls). [REDACTED]

The matching process will be conducted after 6-month study data (or early termination data, if applicable) is collected for all Abilify MyCite patients. The virtual matched control group identified in this process will be used for all study analyses with a small amount of attrition expected for the 12-month analyses for controls who no longer have Anthem insurance coverage.

A pool of potential controls will first be identified using the following criteria:

- ≥ 1 day of enrollment in an Anthem-affiliated commercial, Medicaid, or Medicare health plan with medical and pharmacy benefits during the observation period (from date of First Patient In up until date of Last Patient In)¹³.
- ≥ 1 pharmacy claim for any atypical antipsychotic (excluding Abilify MyCite, clozapine, and long-acting injectable antipsychotics [LAIs]^{14,15}) during the observation period (Appendix F, Tables 2a and 2b).

¹³ Timeframe may be extended if additional samples are needed.

¹⁴ LAIs include: Aripiprazole monohydrate (Abilify Mantenna), Aripiprazole lauroxil (Aristada), Olanzapine pamoate (Zyprexa Relprevv), Paliperidone palmitate (Invega Sustenna), Paliperidone palmitate (Invega Tri state), Risperidone microspheres (Risperdal Consta)

¹⁵ Drugs include: Aripiprazole, Asenapine, Brexpiprazole, Cariprazine, Iloperidone, Paliperidone, Pimavanserin tartrate, Quetiapine fumarate, Risperidone, Ziprasidone, Ziprasidone Mesylate

- ≥ 1 all-cause hospitalization or partial psychiatric hospitalization¹⁶ that occurs at most 60 days prior to a pharmacy claim for any atypical antipsychotic (excluding Abilify MyCite, clozapine, and LAIs).
 - The earliest such pharmacy claim observed after the earliest observed hospitalization will be set as the initial (temporary) index date for each potential control.
 - For patients with ≥ 2 qualifying hospitalization/pharmacy claim episodes, an iterative process will be used to find the best match, and the final index date will be assigned accordingly.
- Age 18 to 63 on index date.
- ≥ 1 claim for SCH, BP1, or MDD on or before index date.
- No claims for pregnancy during the observation period.
- No claims for any LAI during the observation period.
- ≥ 180 days of medical and pharmacy enrollment prior to index date

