- ≥ 180 days of medical and pharmacy enrollment following index date

Prior to matching, the pool of potential controls and the Abilify MyCite cohort will be stratified by psychiatric diagnosis (SCH, BP1, MDD). The Abilify MyCite cohort psychiatric diagnosis will be based on the psychiatric diagnosis recorded in the eCRF. The potential controls psychiatric diagnosis will be based on the psychiatric diagnosis identified [REDACTED] CCI. In the event that more than one of the qualifying psychiatric diagnoses is identified [REDACTED] CCI, the following hierarchy will be applied to potential controls: SCH>BP1>MDD.

From this pool of patients, combined with the active arm, logistic regression will be used within each psychiatric diagnosis to estimate a propensity score for each patient, where propensity refers to a patient's pre-index likelihood to be in the active arm. The dependent variable equals 1 for patients in the active arm and 0 for the controls. The following variables may be considered for inclusion in the propensity score model; a final determination will be made using descriptive study results on patient baseline characteristics.

- Age
- Gender
- Month of index date
- Plan type (commercial, Medicaid, or Medicare health plan with medical and pharmacy benefits)
- Number of fills for any atypical antipsychotic over 6-12 months prior to index date
- [REDACTED] CCI
- Occurrence/number of visits with a psychiatrist over 6-12 months prior to index date
- Comorbidities over 6-12 months prior to index date

¹⁶ Defined as a medical claim with place of service code = 52 ("Psychiatric Hospitalization"), or with HCPCS codes H0035 or S0201.

- Region of patient residence (Northeast, South, Midwest, West)

The estimated propensity scores will be used to match active arm patients to the virtual controls in a 1:3 ratio. Prior to assessing outcomes, the validity of the propensity score adjustment will be assessed by (1) graphically examining the overlap in propensity scores across treatment and control groups¹⁷, and (2) comparing balance in all baseline characteristics across the cohorts via standardized mean differences. A standardized mean difference >10% in absolute value will be used to indicate potential imbalance that may warrant further investigation or adjustment (e.g. through regression analysis).¹⁸ Propensity score models will be finalized prior to the assessment of outcomes.

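### Antipsychotic switching before baseline is built into the MyCite arm, but no visible matching variable for the controls captures a switch between drugs

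*Protocol*

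**What the plan says.** **MyCite arm.** Protocol 3.3.4 admits "Patients currently prescribed aripiprazole, or appropriate for aripiprazole treatment", so the arm mixes current users with patients on something else. Protocol 3.1.1 and 3.5.1.3 direct that "those not on aripiprazole at screening will use the screening period for conversion to aripiprazole from other antipsychotics according to the approved labels", within a screening period of up to 13 days. Protocol 3.5.1.2 places the judgement that aripiprazole is appropriate, and the initiation of MyCite, before and independent of the study, but makes that judgement "regardless of whether or not they would switch from current treatment".

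**Controls.** Protocol 3.1.1 describes their treatment as "any product other than Abilify MyCite, which may be oral aripiprazole or any other product". SAP 3.4 requires at least one atypical antipsychotic claim no more than 60 days after a hospitalization or psychiatric partial hospitalization. It then states: "The earliest such pharmacy claim observed after the earliest observed hospitalization will be set as the initial (temporary) index date". Patients with two or more qualifying episodes are re-indexed iteratively to find the best match. No rule requires the index claim to be a new start or a change of drug.

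**Matching and analysis.** Matching is stratified by diagnosis. The visible propensity candidates in SAP 3.4 are age, gender, index month, plan type, psychiatrist visits, comorbidities, region and "Number of fills for any atypical antipsychotic over 6-12 months prior to index date". One further candidate is redacted. The list is provisional and is to be finalised before outcomes are assessed. Standardized differences above 10% may lead to adjustment. The primary test is unadjusted in both documents: independent proportions in Protocol 7.3.1, McNemar in SAP 4.4.

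**The concern.** A recent change of antipsychotic is plausibly related to hospitalization over the next months. The plan produces such changes in one arm, just before follow-up starts, and does not select controls on the same event. A MyCite patient with six fills of drug A who was then converted to aripiprazole has the same fill count as a control with six fills of drug A who simply refills it. The two can be matched as equals although one has just changed drug.

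This is separate from which drug is taken. It would remain if every control were on aripiprazole, because the difference lies in having recently changed. Protocol 2.1 attributes the expected benefit to treatment decisions based on objective ingestion data, so a drug change at entry is a different cause that the comparison would mix with the device effect. At stake is whether a difference in 180-day hospitalization, or the lack of one, can be attributed to MyCite.

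**Working it through.** **1. What the fill count can and cannot separate**

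| Status at index | Prior atypical fills | Separated by the count? |
|---|---|---|
| Continuing the same drug | More than zero | No, looks like a switch |
| Switched between atypicals | More than zero | No, looks like continuing |
| Newly started on an atypical | Zero | Yes |

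The gap therefore concerns switching between drugs, not new starts.

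**2. Inputs** (Protocol 7.1, SAP 4.2): rates 29.04% and 36.30%, a difference of 7.26 points; 1:3 ratio; 80% power; significance level 0.025, taken as one-sided because the hypothesis is directional; unpooled Z-test; 447 completers; 30% dropout; 640 enrolled.

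**3. The plan's own figures**

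- Unpooled, as named: n = (1.960 + 0.842)² × (0.2904×0.7096 + 0.363×0.637/3) / 0.0726² = 421.6, so 422. The pooled form gives 441 and the continuity-corrected form 459. The stated 447 is within 3% of these two but not of the unpooled result.
- Enrolment: 447/0.70 = 638.6, so 639 against the stated 640.
- Controls: 3 × 447 = 1341, against approximately 1350.

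These figures only calibrate the sensitivity check below.

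**4. Power without bias**

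SE = √(0.2904×0.7096/447 + 0.363×0.637/1341) = 0.02517

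Power = Φ(0.0726/0.02517 − 1.96) = 82.2%

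**5. Illustration if switching raises risk**

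Net bias = s × d, where s is the difference between arms in the share recently switched and d is the excess hospitalization rate in switchers. Neither is in the documents. For example, s = 20 points with d = 5 points gives 1 point, and s = 20 with d = 10 gives 2 points.

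Power = Φ((0.0726 − bias)/0.02517 − 1.96)

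| Net bias against MyCite | Share of the 7.26-point effect | Power |
|---|---|---|
| 0 | 0% | 82.2% |
| 0.5 points | 7% | about 77% |
| 1 point | 14% | 70.1% |
| 2 points | 28% | 55.2% |

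The size is driven by the assumptions. With 25% of MyCite patients and no controls switched, and a relative risk of 1.1, the bias is 36.3 × 0.25 × 0.1 = 0.9 points. With 50% and none, and a relative risk of 1.5, it is 36.3 × 0.5 × 0.5 = 9.1 points.

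**6. Illustration if switching lowers risk**

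Take 50% versus 0% switched and a relative risk of 0.9. With a device of no effect, the MyCite rate is 36.3% × (1 − 0.5×0.1) = 34.5%. The chance of declaring superiority is then about 10% instead of 2.5%.

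**The case against.** Several points on the other side stand and limit the concern.

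- **New starts are visible.** Half the expected sample is MDD (Protocol 7.1), where aripiprazole is adjunctive (Protocol 1). MDD patients on no antipsychotic would be new starters with a zero count. A reader might infer that nothing separates continuing patients from any kind of change, but that is too broad.
- **Controls may have changed drug too.** Both arms need a recent hospitalization, and a control's first fill afterwards may be a start or a switch. Only the difference in shares matters, and it is unknown.
- **The cause of the switch is not settled.** A reader might infer that patients are switched only because they enrol. Protocol 3.5.1.2 makes the treatment judgement independent of the study, although its wording leaves room for switches that accompany enrolment. This bears on motive; it does not make the controls comparable.
- **Redaction.** Besides the redacted covariate, which follows the fill count in the list, most of Protocol 3.5.4 on the control group is blacked out. It cannot be shown that a switch variable is absent, only that none is visible.
- **The balance check is open.** It covers all baseline characteristics, and medication data are collected. A reader might infer that the check could never flag switching. More exactly, switch status is not named or defined for it.
- **Pragmatic contrast.** One can argue that starting aripiprazole is part of a product-versus-usual-care strategy. That would be a defensible estimand, but Protocol 2.1 attributes the expected gain to tracking.

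**Conclusion.** The point holds in a limited form. Conversion before baseline is specified for MyCite patients not already on aripiprazole, a control's index fill may be a refill, and the visible fill count cannot identify a change between drugs. Unless a redacted item covers it, recent switching is left unbalanced before an unadjusted test.

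The size is not known. A loss of power from about 82% to 70% or 55% rests on an assumed net bias of 1 or 2 points and on the planned rates and sample sizes. A reader might infer that the bias runs against MyCite, or that it could cancel the whole 7.26-point effect. The documents support neither: they give no share switched and no risk after a switch, and with a lower risk the bias favours MyCite.

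SAP 5.0 records that the study stopped after two patients with no efficacy assessment. The point therefore concerns the design as written and any reuse of it, not a result. It is a worthwhile improvement at low cost.

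**What to change.** In SAP 3.4, derive index antipsychotic status in both arms with three levels: continuing the same drug, switched, newly started. Use pre-index fills for both arms, plus site-recorded medication for MyCite patients, and count conversion during screening as a switch. Force the variable into the propensity model within each diagnosis, report its standardized difference in the balance table, and adjust for it by regression if that exceeds 10%.

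The data should allow this. Controls need at least 180 days of prior pharmacy enrolment. Protocol 3.3.4 sets no such minimum for MyCite patients, so the site record matters for them.

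Use exact matching on this variable only if the 1:3 ratio is kept. SAP 4.2 allows the ratio to fall to 1:2 or 1:1 when controls run short. By the same unpooled formula at 447 MyCite patients:

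- 1:2 (894 controls): SE = 0.02683, power about 77%
- 1:1 (447 controls): SE = 0.03128, power about 64%

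Falling to 1:1 would cost more power than a 1-point bias (70%).

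The cost is one derived variable, some SAP wording and possibly harder matching for switched patients. The covariate list is still open until outcomes are assessed, so the change fits the SAP's own process and alters no treatment rule.

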3.5.1.4 Main Study: Baseline

The baseline visit marks the beginning of the interventional phase. Patients will receive training and onboarding with Abilify MyCite as outlined in [Table 3.5.1-1](#). Training will be based on the commercial training materials for Abilify MyCite to reflect real-world practice. Baseline assessments will include: demographic data, medical and psychiatric history, height, weight, vital signs, and hospitalization history (all-cause and psychiatric).

CCI [REDACTED]

3.5.1.5 Main Study: Treatments

Patients will initiate Abilify MyCite upon study enrollment (at the baseline visit) and will continue use through Day 90 (with an optional second use period over Days 180-≤360),

as deemed clinically appropriate by their treating physician. Abilify MyCite may be started and stopped as clinically appropriate based on physician judgment. Ability MyCite metrics will be captured throughout use.

During periods of nonuse of Abilify MyCite, the patient continues with oral aripiprazole or other appropriate treatment, per routine clinical care.

